3 OBJECTIVES

3.1 Study Objectives

Primary Aims:

1. To test the efficacy of the OHT intervention in a theory-based, fully powered, dose-matched design with objective clinical measurement of caries. Parents of children <7 years old attending one of our partner pediatric clinics will be randomized to receive either OHT or CWT. H₁: Those receiving OHT will have lower 24- month incidence of caries vs. those receiving CWT, as assessed by clinical exam. Clinical exams will take place at baseline and 12-and 24- months later.
2. To assess the mechanisms through which intervention effects occur (mediators). H₂: OHT will differentially change Social Cognitive Theory constructs (motivation, self-efficacy, outcome expectations) over time vs. CWT. We will test the mediational effect on caries. Mechanisms will be assessed through text messaging assessments during the intervention, and through self-report surveys at baseline, and 2, 4, 12 and 24- months after baseline.

Secondary Aims:

1. To perform budget impact analyses of pediatric clinic adoption of the OHT intervention to determine the financial consequences of adoption, diffusion, and sustainability. The budget impact analyses will include interviews with key stakeholders.
2. Examine change in pediatric oral health behaviors (e.g. tooth brushing, diet, sugar sweetened beverages, fluoride toothpaste use, preventive dental visits, and 'lift the lip' oral assessment by parents). These variables will be assessed at baseline, 4, 12, and 24 months after baseline.
3. To assess the effect of the intervention on the parent's oral health status, knowledge, attitudes, and behaviors (spill-over effect). These variables will be assessed at baseline, 4, 12, and 24 months after baseline.
4. To identify subpopulations for whom the intervention has the greatest effect (moderators; e.g., race/ethnicity, insurance coverage, parent educational level, parent depressed mood, child's prior caries experience and intervention dose/engagement). All moderators will be assessed at baseline, except for intervention dose/engagement, which will be assessed during the course of text message delivery.

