12 STATISTICAL CONSIDERATIONS

12.1 Study Hypotheses

Primary hypothesis 1: Those receiving OHT will have lower 24 month incidence of any new caries, compared to those receiving CWT.

Primary hypothesis 2: The OHT effect on new caries at 24 months will be mediated through Social Cognitive Theory constructs (self-efficacy, motivation, and outcome expectations). We will examine indirect effects of OHT through self-efficacy, motivation, and outcome expectations at 2 months, to potentially increased motivation and oral health behavior at 4 months (end of intervention) to new caries at 12 and 24 months. We will also examine indirect effects of OHT through self-efficacy, motivation, and outcome expectations at 4 months (end of treatment), to potentially increased motivation and oral health behavior at 12 months and to new caries at 12 and 24 months.

Secondary hypothesis 1: We hypothesize that the total cost of OHT implementation will be more cost-effective than standard of care (e.g., oral health anticipatory guidance).

Secondary hypothesis 2: Those receiving OHT will have better pediatric oral health behaviors (tooth brushing, diet, sugar-sweetened beverages, fluoride toothpaste use, preventive dental visits, and oral assessment by parents) at 4 months (end of intervention), 12 months, and 24 months, compared to those receiving CWT.

Secondary hypothesis 3: Those receiving OHT will have better oral health behaviors (tooth brushing, dental visits), oral health knowledge, and attitudes at 4 months (end of intervention), 12 months, and 24 months, compared to those receiving CWT.

Exploratory Analyses: These analyses will explore whether the effect of OHT vs. CWT on new caries at 24 months is greater in subpopulations defined by race/ethnicity, insurance coverage, parent education level, child's prior caries experience, parent depressed mood, and intervention dose/engagement.

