12.4 Final Analysis Plan

Overview of Analytic Plan: Primary analyses will focus on the comparison of those assigned to OHT vs. CWT on oral health and behavior outcomes using all available data (i.e., restricted to those followed) and, following the intent-to-treat principle, randomized subjects will be included in the analysis regardless of their compliance with the study protocol and engagement in the study interventions. While no differences between study arms are anticipated due to randomization, preliminary analyses will explore differences between arms and variables found to differ between groups (at the $p<0.10$ level) will be adjusted for in analysis. For dichotomous outcome variables (e.g., incidence of any new caries at 24 months; use of fluoride toothpaste) analyses will use logistic regression models, with intervention effects reported as odds ratios

with 95% confidence intervals. Count data (e.g., number of new caries at 24 months) will be analyzed through Poisson regression models, if the distributional assumptions of the Poisson model are met, or negative binomial or zero-inflated models if the outcome distribution better meets the assumptions of these models. Results will be reported as rate ratios with 95% confidence intervals. Continuous variables (e.g., number of tooth brushings per week) will be analyzed through mixed effects linear regression models. Data will also be analyzed by race and gender as specified in the Notice of Grant Award, although these analyses will be exploratory due to lack of power. If follow-up falls below the anticipated 70%, primary analyses will account for missing data through inverse probability weighting using propensity scores for missingness. If follow-up meets the anticipated 70%, inverse probability weighting may be used in sensitivity analyses addressing the impact of missing data.

The two-tailed alpha 0.05 level will be used to indicate statistical significance.

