
Aims 2 and 3. We will compare changes in these behaviors over time in OHT vs. CWT using mixed effects logistic regression models (for dichotomous outcomes) and mixed effects linear regression models (for continuous outcomes). Changes in these behaviors from baseline to 2, 4, 12, and 24 months will be described through odds ratios and 95% confidence intervals for logistic models, and slopes for linear models. Differences in changes over time for OHT vs. CWT will be tested through group by time interaction terms.

Aim 4: To identify subpopulations for whom the intervention has the greatest effect, we will analyze moderators; e.g., race/ethnicity, insurance coverage, parent educational level, and child's prior caries experience. This aim focuses on moderator effects (also known as effect modification) for incident caries over 24 months. We will use logistic regression models with multiplicative interaction terms (treatment group x moderator) to compare the efficacy of OHT across subpopulations.

17. Missing data: We will gather follow-up information and reasons for dropout regardless of treatment completion, censoring at the point of loss. We will examine the extent of drop-out, and identify characteristics associated with drop-out through logistic regression. Given drop-out does not exceed the expected rate of 30%, primary analyses will be based on available data. Secondary analyses will account for missing data and explore the potential impact of drop-out on study findings. We will describe the robustness of our findings with respect to missing data using inverse probability weighting. This approach to handling missing data has two steps: 1) develop propensity scores for missing data, which involves using logistic regression to model the probability of being followed to the 24 month visit as a function of baseline variables, including history of caries; and 2) using the inverse of the propensity scores (predicted probabilities from the first step) to serve as weights in our logistic regression model of new

primary teeth caries. Provided the data are missing at random (MAR), that is, the probability of missingness can be fully explained by observable data, this approach produces asymptotically unbiased estimates. If there is sufficient missing data, and a concern that data may be missing not at random, we will also consider pattern mixture models to perform a sensitivity analysis of the potential impact of missingness.

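### For continuous secondary behaviour outcomes, a common baseline mean or baseline as a covariate would give a tighter arm comparison than the planned difference in change, at no data cost

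*Combined protocol and SAP*

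**What the plan says.** Section 12.4 (Aims 2 and 3) compares the arms on behaviour over time "using mixed effects logistic regression models (for dichotomous outcomes) and mixed effects linear regression models (for continuous outcomes"). It continues: "Changes in these behaviors from baseline to 2, 4, 12, and 24 months will be described through odds ratios and 95% confidence intervals for logistic" regression; the linear analyses are summarised by slopes. The test is then given: "Differences in changes over time for OHT vs. CWT will be tested through group by time interaction terms". The model is not written out. Nothing in that paragraph enters the baseline value as a covariate or sets the two arms' baseline means equal.

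Three other statements in the overview of Section 12.4 bear on this:

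- Covariates: "preliminary analyses will explore differences between arms and variables found to differ between groups" at p<0.10 are adjusted for.
- Analysis set: analyses are made "using all available data (i.e., restricted to those followed").
- Significance: "The two-tailed alpha 0.05 level will be used to indicate statistical significance".

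Secondary hypothesis 2 in Section 12.1 is about status at a visit: "Those receiving OHT will have better pediatric oral health behaviors" at 4, 12 and 24 months. Secondary hypothesis 3 has the same form for the parent. Section 3.1 says of both sets of variables: "These variables will be assessed at baseline, 4, 12, and 24 months after baseline". Section 3.2.2 also collects some behaviours at 2 months.

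Sections 5.3, 5.4.1 and 7.2 all place the baseline questionnaire before randomisation.

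**The concern.** When baseline is one of the outcome times and the arm effect is a group-by-time term, the ordinary model also carries a group main effect. Each arm then has its own baseline mean, and the contrast at a visit is follow-up minus baseline in one arm, less the same in the other. Randomisation guarantees that the two true baseline means are equal. Estimating both spends information on a difference known to be zero and carries any chance baseline imbalance fully into the result.

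The cost is a wider interval for every continuous behaviour outcome under secondary hypotheses 2 and 3. Section 12.2 states no power for these outcomes, so the plan does not show that there is precision to spare.

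**Working it through.** **Inputs from the documents.** Section 12.2: 425 dyads randomised and 300 analysed per arm, with 70% followed at 24 months. Section 12.4: two-sided 0.05.

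**Assumptions, not in the documents.** Correlation r between baseline and follow-up of 0.3, 0.5 or 0.7; equal variances at all visits; for the slope model, equal correlation between all visits and complete data; for the power illustration, an effect of 0.2 SD.

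**1. Nearest stated figure.** The plan gives no power, SD or correlation for any behaviour outcome. Its only power figures are for caries. For 23.8% against 14.3% with 300 per arm, the standard two-proportion calculation gives 0.8438, which agrees with the stated 84%. This checks the plan's sample-size arithmetic and says nothing about Aims 2 and 3.

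**2. One visit, complete pairs.** Per-arm variance in SD² units is 2(1−r) for change and 1−r² for the baseline-adjusted contrast. The ratio is (1+r)/2, so the share saved is (1−r)/2. This is positive for every r below 1.

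**3. All randomised baselines kept, fraction f = 0.7 followed.** In units of SD² per randomised dyad, the free-baseline variance is (1−r²)/f + (1−r)², and the common-baseline variance is (1−r²)/f. At r = 0.5: 0.75/0.7 = 1.071, plus 0.25 gives 1.321, so the saving is 0.25/1.321 = 19%.

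**4. Linear slope by arm.** Let A = X′V⁻¹X, with X holding an intercept and time in months and V the visit correlation matrix. The slope variance is proportional to [A⁻¹]₂₂ with free intercepts and to 1/A₂₂ with a common intercept, so the saving is A₁₂²/(A₁₁A₂₂). At r = 0.5 with visits at 0, 2, 4, 12 and 24 months: A₁₁ = 1.667, A₁₂ = 14, A₂₂ = 892, and 196/1,486.7 = 13.2%. The four-visit version omits month 2.

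| Assumed r | 2(1−r) | 1−r² | Saved: one visit, complete pairs | Saved: all baselines kept, 70% followed | Saved: slope, 5 visits | Saved: slope, 4 visits |
|---|---|---|---|---|---|---|
| 0.3 | 1.40 | 0.91 | 35% | 27% | 22.5% | 30.5% |
| 0.5 | 1.00 | 0.75 | 25% | 19% | 13.2% | 19.2% |
| 0.7 | 0.60 | 0.51 | 15% | 11% | 6.7% | 10.3% |

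A simulation (6,000 runs, 425 randomised and 298 followed per arm) gave 33%, 25% and 14% for complete pairs, and 26%, 18% and 11% with all baselines kept.

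**5. What the complete-pairs saving is worth.** Dividing 1 by 0.65, 0.75 and 0.85 gives 1.54, 1.33 and 1.18, equivalent to 54%, 33% or 18% more dyads. For power, SE = √(variance × 2/300) and power = Φ(0.2/SE − 1.96). With the assumed 0.2 SD effect, power rises from 54% to 73% (r = 0.3), from 69% to 81% (r = 0.5) and from 89% to 93% (r = 0.7). The 300 per arm is the 24-month caries figure; no number is stated for the surveys at earlier visits.

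**The case against.** **The separate baseline means are inferred.** A constrained longitudinal model also tests its arm effect through group-by-time terms; it only drops the group main effect. The sentence in Section 12.4 is therefore compatible with the remedy. This stands: the free baseline is the usual reading, not a written specification. But no section specifies a common baseline or a baseline covariate, so the sentence is needed either way.

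**Aim 2 is to examine change, so testing change is coherent.** True, and the planned test is valid. A reader might infer bias or an inflated error rate; the documents do not support that. Under randomisation the arm difference in change and the arm difference at the visit have the same expectation for a continuous outcome. Only the precision differs.

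**The p<0.10 rule already deals with imbalance.** It acts only when a variable happens to differ between arms, whereas the precision gain exists whether or not it does. The rule also does not say how a baseline value that is already an outcome record would become a covariate.

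**The size is not a property of this trial.** A reader might take 15% to 35% as this trial's loss. That range needs an assumed r of 0.7 to 0.3, one visit and complete pairs. Restriction to those followed supports the complete-pairs case, but the reference to slopes points to smaller figures.

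**Some outcomes are dichotomous.** A reader might carry the percentages over to the mixed logistic models. The variance formula does not hold there, and adding baseline as a covariate changes which conditional odds ratio is estimated.

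**Conclusion.** The point holds as a free improvement in precision for the continuous outcomes of Aims 2 and 3. The direction is certain for any r below 1, given baseline before randomisation and equal variances. The size depends on an r that the documents do not give: for r from 0.3 to 0.7, the saving runs from about 7% (slope model, five visits, r = 0.7) to 35% (one visit, complete pairs, r = 0.3).

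This is not an error in the plan. The primary caries analysis is a separate logistic model that already controls for age and previous caries, and it is unaffected. No gain has been calculated for the dichotomous behaviour outcomes.

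**What to change.** In Section 12.4, Aims 2 and 3, state the baseline handling for continuous outcomes in one of two ways:

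- a constrained longitudinal model, with no group main effect at baseline, visit as a categorical factor, and the baselines of all randomised dyads kept; or
- a mixed model of the post-baseline visits only, with the baseline value as a covariate.

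In either case, report the arm difference with its 95% confidence interval at 4, 12 and 24 months, so that the analysis answers secondary hypotheses 2 and 3 directly. If a common baseline mean was always intended, one sentence saying so is enough.

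The same handling may be used in the mixed logistic models, provided the text says which conditional odds ratio is being estimated.

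The cost is SAP wording only, with no new data. One caution: if only followed dyads are analysed, a common baseline mean also assumes that dropout does not differ by arm in relation to baseline. Keeping all randomised baselines, or using baseline as a covariate, eases that.

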All caregivers will receive a "report card" providing a summary of untreated dental decay found and a recommendation regarding the timing for seeking care. All caregivers are offered help in making a dental appointment and study staff will proactively follow up in cases with pain or infection to facilitate dental treatment.

To prevent TM related injury, participants will be told that they should not view, send, or receive texts while driving or walking. During the pilot phase, there were no adverse events reported.

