3.2 Study Outcome Measures

3.2.1 *Primary*

Caries Incidence: Tooth surface level data in children, collected by calibrated clinical examiners (blind to treatment condition), utilizing the OHDC Modified ICDAS methodology, will allow calculation of caries incidence rates (development of a new cavitated lesion or filled surface in a previously sound tooth surface or tooth surface without a cavitated lesion). Data will be collected by clinical examiners at baseline, 12, and 24- months.

Mediators:

Self-efficacy to perform oral health behaviors (12 items). The overall self-efficacy score represents how sure participants are that they can engage in recommended behavior to take care of their children's teeth. The overall self-efficacy score is the mean response. Items are scored on a 1-7 scale, 1 = not sure at all to 7 = extremely sure. This measure will be assessed at all measurement points (baseline and 2, 4, 12, 24 months) (Cronbach's alpha = .92). A one-item measure of this construct will be assessed during the TM program.

Motivation to perform oral health behaviors (12 items). The overall motivation score represents how much participants want to engage in recommended behavior to take care of their children's teeth. The overall motivation score is the mean response. Items are scored on a 1-7 scale, 1 = do not want to at all to 7 = very much want to. This measure will be assessed at all measurement points (Cronbach's alpha = .88). A one-item measure of this construct will be assessed during the TM program.

Outcome expectations regarding oral health behaviors. This measure assesses the degree to which participants perceive that performing the oral health behaviors (e.g., brushing) will lead to the desired outcome (e.g., reduced dental caries) in their children (Stewart et al., 1997). This measure will be assessed at all measurement points. A one-item measure of this construct will be assessed during the TM program.

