4 STUDY DESIGN

This is a 2-arm, randomized controlled Phase III, single-center longitudinal trial. 850 parents or caregivers of children (< 7 years old) and their children with pediatric appointments at four targeted urban clinics will be recruited, consented, and subsequently randomized to OHT or CWT. We hypothesize that those randomized to the OHT group will have reduced incidence of caries as assessed by objective clinical exam 24- months after a baseline exam. Randomization will be a permuted block design, stratified by study site (Codman Square, Dorchester House, BMC, South End Community Health Center), and history of caries (no history of caries, any caries). Because of the sparsity of Spanish speaking participants, with Spanish speakers primarily concentrated at one site, we will not stratify by site language (English, Spanish) but only on caries history to yield 8 strata. CWT and OHT intervention arms will be matched on TM dose, duration and frequency, and employ identical features and engagement strategies for strong internal validity. External validity will be supported by the fact that participants will be proactively recruited from an existing channel (pediatric clinic appointments) and use of the text message program in their everyday lives. Recruitment sites are located in urban, low-income areas, and the population is ethnically diverse and on public assistance.

The approximate time to complete study enrollment is 1- year and the expected duration of subject participation is 2- years. A clinical exam to assess caries will take place at baseline and 12 and 24- months later. Clinical examiners are study staff and will be calibrated and blinded. Self-report surveys will take place at these time points, plus 2 and 4- months after baseline. These data will be captured through electronic data entry, in person, over the phone, or through an on-line link. Weekly and monthly assessments will also occur during the 4- month TM program (from baseline through 4-months post-baseline). The coordinating center (CC) will be University of California at San Francisco.

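### The missing-data weights use baseline variables only and leave out the 12-month caries exam, although their justification rests on all observable data

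*Combined protocol and SAP*

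**What the plan says.** Section 12.4 (Final Analysis Plan) bases the primary comparison on children with follow-up, "using all available data (i.e., restricted to those followed". For drop-out, its missing-data paragraph sets out two steps. The first is a logistic regression to "model the probability of being followed to the 24 month visit as a function of baseline variables, including history of caries". The second uses the inverse of the predicted probabilities as weights in the model for new caries in primary teeth. The estimates are said to be asymptotically unbiased under this condition: "Provided the data are missing at random (MAR), that is, the probability of missingness can be fully explained by observable data".

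The weighting has two roles. At 70% follow-up or more it supports sensitivity analyses. Otherwise: "If follow-up falls below the anticipated 70%, primary analyses will account for missing data through inverse probability weighting using propensity scores for missingness". That sentence names the method but lists no covariates.

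Section 3.2.1 says of the caries outcome: "Data will be collected by clinical examiners at baseline, 12, and 24- months". An event is "development of a new cavitated lesion or filled surface in a previously sound tooth surface or tooth surface without a cavitated lesion", and the primary analysis compares any with no new caries over 24 months.

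**The concern.** Weights that use only baseline variables remove bias when, given those variables, being seen at 24 months is unrelated to the outcome. The condition in Section 12.4 is wider: missingness may depend on anything observed. The 12-month exam is observed, and it is closely tied to the outcome, because new caries recorded at 12 months already counts as new caries over 24 months. If a family's return depends on that finding, the data can meet the stated condition while the planned weights fail.

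There is a documented route by which the finding could affect return. Under Section 2.3.1 every caregiver gets a report card "providing a summary of untreated dental decay found and a recommendation regarding the timing for seeking care". This overlaps with the outcome but is not the same, since a new filled surface counts as an event and is not untreated decay.

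At stake is the safeguard. The plan turns to weighting when losses exceed expectation. Against this mechanism the weights would give nearly the same answer as the unweighted analysis.

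**Working it through.** **1. The plan's own figure.** Pooled two-sided chi-square formula, 23.8% vs 14.3%, 300 per arm, alpha 0.05: power 0.844, against 84% in Section 12.2. The sample size is not in dispute. The plan gives no figure for the weighting.

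**2. Inputs.** From Section 12.2: 425 per arm, control incidence 23.8%, expected follow-up 70%. Assumptions that are not in the documents:
- the hazard is constant over two equal intervals;
- families lost by 12 months stay lost;
- 82% are seen at 12 months and 71% at 24 months, or 75% and 62%;
- in the OHT arm only, new caries observed at 12 months multiplies the odds of return by 1/2 (heavier case: 1/3).

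**3. Closed form under the null, no baseline covariate.** The chance of new caries per interval is h = 1 − √0.762 = 0.127. Let r be the probability of return for a child seen at 12 months, and q that probability after the odds are cut. Among OHT completers:

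odds = [h·q + h(1 − h)·r] / [(1 − h)²·r], and OR = odds / (0.238/0.762).

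- 71%: r = 0.71/0.82 = 0.866. Halved odds give q = 0.763, odds = 0.2926, OR = 0.2926/0.3123 = 0.937. One-third odds give q = 0.683, OR = 0.887.
- 62%: r = 0.62/0.75 = 0.827. Halved odds give q = 0.705, OR = 0.921. One-third odds give q = 0.614, OR = 0.863.

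Here baseline-only weights are constant, so they leave these values unchanged.

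**4. Scale at 71%, halved odds.** OHT children with observed 12-month caries: 425 × 0.82 × 0.127 = about 44. Extra lost: 44 × (0.866 − 0.763) = about 4.5. SE of the log OR at 302 per arm: √[2/(302 × 0.238 × 0.762)] = 0.19. Shift: |ln 0.937|/0.19 = 0.34 SE. Type I error: Φ(0.34 − 1.96) + Φ(−0.34 − 1.96) = about 6.3%. At 62% (about 263 per arm, SE 0.205) the shift is 0.40 SE and the error about 6.9%.

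**5. Simulation.** 8,004 trials per scenario, unadjusted OR, with a baseline covariate that affects both caries (log hazard 0.5 per SD) and attendance (log odds −0.3 per SD). Null, OHT return odds halved (one third):

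| Follow-up | Method | OR | Type I error |
|---|---|---|---|
| 71% | completers | 0.93 (0.88) | 6.2% (10.2%) |
| 71% | planned weights | 0.93 (0.88) | 6.2% (10.3%) |
| 71% | imputation using 12-month exam | 1.00 (1.00) | 5.1% (4.8%) |
| 62% | planned weights | 0.91 (0.85) | 7.0% (11.7%) |
| 62% | imputation using 12-month exam | 1.00 (1.00) | 4.5% (5.1%) |

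If halved odds apply only to the 70% (50%) of positives with untreated decay on the card, the weights give OR 0.95 (0.96) and 5.7% (4.9%) at 71%.

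**6. Opposite direction.** Planned effect, odds halved in the child wellness text (CWT) arm only, 71%: the weights give OR 0.57 instead of 0.53, and power 72% instead of 84%.

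**7. Equal dependence.** With odds halved in both arms under the planned effect, the step 3 formula gives completer incidences of 22.6% and 13.5% instead of 23.8% and 14.3%, and OR 0.535 against 0.534. Simulated type I error under the null with equal halving: 4.3–5.0%.

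**8. What the exam cannot repair.** In these scenarios 18 of 29 points of loss (62%), or 25 of 38 (66%), occur before the 12-month exam. Suppose OHT children with new caries have half the odds of attending at 12 months (0.82 falls to 0.695). Within-arm imputation then puts 12-month incidence at 0.127 × 0.695 / (0.127 × 0.695 + 0.873 × 0.82) = 11.0% instead of 12.7%. The 24-month figure becomes 0.110 + 0.890 × 0.127 = 22.3%, and OR 0.92.

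**The case against.** The strongest reply is that the OR moves only if return after 12-month caries differs by arm, and the design gives little reason to expect that. The arms are "matched on TM dose, duration and frequency, and employ identical features and engagement strategies" (Section 4). Payments and cohort maintenance are the same (5.3), data-collecting staff are masked (5.4.2), and the report card goes to all caregivers. The only arm-specific route is the content of the messages, including the booster after the 12-month assessment. The size of the bias comes from assumed inputs, and the simulations are unadjusted whereas the planned model controls for age and previous caries. The missing-data paragraph also plans to look for characteristics associated with drop-out, not expressly limited to baseline, and to consider pattern mixture models. All of this stands, and it limits the priority. It does not close the gap: the drop-out description does not feed the weights, and pattern mixture models are optional and kept for data missing not at random.

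A reader might infer that the plan expressly confines the below-70% primary analysis to baseline variables. It does not. That rule lists no covariates, and the missing-data paragraph is simply the only specification available.

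A reader might also infer that the 12-month exam would remove the bias from drop-out. Step 8 shows otherwise: it repairs only loss that depends on what was seen at that exam.

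**Conclusion.** The mismatch is in the text and needs no simulation: the weight model is narrower than the assumption offered for it, and it omits an observed reading of the primary outcome. The consequence for the OR is conditional. It requires arm-differential return after observed 12-month caries, which the documents neither show nor exclude. Given that, completers and planned weights are off by about the same amount, in either direction. With halved odds in one arm this is 0.3 to 0.4 SE, with type I error of 6% to 7%. Errors of 10% to 12% need odds of one third in one arm only, which nothing in the documents supports. With equal dependence only the arm incidences are too low.

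It would be tempting to conclude that the primary result is biased or the trial's error rate compromised. The documents do not support that. This is a cheap improvement to the missing-data plan.

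**What to change.** In the missing-data paragraph of Section 12.4, and by reference in its below-70% rule, let the missing-data model use the 12-month exam, by arm, for children who have one. Either form is acceptable:

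- **Multiple imputation within arm.** Impute 12-month status from baseline variables, then 24-month status among children free of new caries at 12 months. Keep observed 12-month new caries as events and combine by Rubin's rules.
- **Sequential weights** with an arm × 12-month caries term. State that children without a 12-month exam are dropped and precision is lower. If attendance at the two exams is unrelated, about 497 children are used instead of about 604, with power 75% against 83% for completers and 87% for imputation.

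Rule out one shortcut: counting lost 12-month positives as events while dropping lost 12-month negatives. In the 71% scenario without dependence, [0.82h + 0.71h(1 − h)] / [0.82h + 0.71h(1 − h) + 0.71(1 − h)²] gives 25.3% instead of 23.8% and, with h = 1 − √0.857, 15.3% instead of 14.3%.

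The cost is a few sentences and modest programming, with no new data. The downsides should be stated: slightly more analysis work, a missing-at-random assumption that remains, and no repair of loss before 12 months that depends on unobserved caries. Keep the pattern mixture models for that.
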